### **Study design including population to be studied, recruitment procedures and available resources**

We propose a non-inferiority randomized clinical trial to enroll 500 Long Term Care residents age 65 and older to receive either Fluvad or HD vaccine at 1:1 ratio. Blood will be sampled pre- and post-vaccine and post-influenza season and coded for blinded laboratory analysis. The FLUBLOK pilot objective will be a substudy of the current AD Fluvad vs. HD Fluzone study (UH IRB 10-27-29), and subjects will be consented on a separate FLUBLOK ICF.

**Population:** 500 subjects age 65 and older living in long-term care facilities in Northeast Ohio area. Up to an additional 120 subjects will be added to FLUBLOK substudy.  
50:50 male:female ratio.

**Study Duration:** 3 years

**Subject Duration:** estimated 6-8 months with patient contact

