### **Recruitment for the FLUBLOK pilot arm for Year 2:**

Any long term care facilities that participated on Year 1 of the study can participate on Year 2, as long as we do not repeat subjects. For the FLUBLOK substudy, we can recruit from those subjects that participated in Year 1 and received either the adjuvanted Fluvad or the HD Fluzone. Since enrolled subjects from Year 1 cannot participate for a 2nd year on the Fluvad vs. HD objective, these previously enrolled subjects would be eligible for recruitment on the FLUBLOK substudy, and therefore, we will use our previously described screening and recruitment methods to consent these subjects for enrollment to receive the FLUBLOK vaccine. We will consent these subjects on a separate FLUBLOK ICF. We may also recruit FLUBLOK subjects from new long term care facility sites that did not previously participate on the study, and we will use the same previously described consenting methods, and consent with the FLUBLOK ICF. If we hit our recruitment goals on the primary endpoint (Fluvad vs HD Fluzone objective), then any additional long term care residents that we may recruit will not be randomized to receive Fluvad or HD Fluzone, but rather will be enrolled in the pilot Aim 4 FLUBLOK arm. These residents will be consented on another ICF, that was modified specifically for FLUBLOK.

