### **Study procedures**

The intervention is randomization to one of the two FDA approved seasonal influenza vaccines (Fluad(AD) and FLUZONE HD (HD)) at 1:1 ratio. The HD vaccine will serve as the control, and the newly FDA-approved AD will be the comparator. We will obtain 20 ml of blood up to 2 weeks prior to the vaccine, or right before the vaccine is given. The second blood draw will be 4 weeks +/- 3 working days post vaccine and the third blood draw of 10 ml will be performed 2-4 weeks after the influenza season is over. The post-season draw may be spread over a two week window because the entire cohort of subjects will need to be drawn during this window, and it may take as long as two weeks to achieve that at all the facilities.

For the FLUBLOK substudy, we will follow the same blood draws and schedule. The subjects recruited to receive the FLUBLOK vaccine will be recruited with the FLUBLOK ICF, and will not be part of the randomization process.

The study will obtain blood work and give a study flu vaccine to consented residents starting in late September, and the third and last blood work will be obtained at the end of the flu season, typically in April. Each subject will then be enrolled as long as 8 months if they are enrolled in September and the flu season lasts until April.

We will obtain the following PHI in the prescreening: name, birthdate, race, ethnicity, gender, facility name and resident location, and whether a resident can self-consent or needs to use the LAR method of consenting. If a resident cannot self-consent, we will obtain the name, mailing address, phone numbers, and relationship of an LAR. We may also collect contact information on a secondary contact/secondary LAR, when appropriate, during the pre-screening process. Some residents may have two LARs/POAs listed in the medical record.

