If the nursing staff ( Director of Nursing, Assistant Director of Nursing, Social Worker, and Unit Nurses) deems that the resident cannot physically or mentally give informed consent, as documented in their facility medical record, we will send an IRB approved Study Consent Form, Letter to LARs, facility Letter of Support, Study Brochure, and addressed stamped envelope to these potential subjects' LARs. We will follow up with a phone call to review the Study Consent Form and if they would like to enroll their family member onto the study, we will ask them to appropriately sign the Consent Form and send it back to us, in the provided envelope. If a resident is physically and mentally able to sign an Assent Form, the study staff will review the Assent Form with the resident. If a subject is determined to be physically or mentally not capable of signing any documents (as documented in their nursing home record and confirmed with either the DON, ADON, or Unity nurse), then we will waive Assent and will file the medical documentation along with the LAR signed written Consent Form. LARs will be mailed a copy of the signed Consent Form for their records, and we will give a copy to the nursing administration at the LTC facility. The Consent Form will have study contact information, so they can withdraw consent at any time.

Waiver of written Assent will not impact subject's safety or rights, as the vaccine being administered is approved by the FDA and administered to all LTC patients per standard of care. If a subject refuses the research blood draw, a later attempt will be made. Subjects who refuse the research blood draw will still remain in the study for data collection.

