To power the A/H3N2-specific analysis, we require 243 per vaccine group or 486 subjects total. With this sample size, we can test non-inferiority in A/H1N1 and A/H3N2 with 80% power. Assuming our observed titers are similar to those from published studies, this sample size will be sufficient to demonstrate superiority of Fluad in A/H1N1. In order to achieve this sample size, we will overenroll by 15%. This degree of over enrollment is informed by prior clinical trial experience and is expected to be adequate given the short time between blood draws and the inclusion criteria of the subjects' expectation, willingness, and ability to have the three blood draws obtained.

For the FLUBLOK pilot studies as there are not sufficient preliminary data to perform a power calculation. That is one of the key reasons why we are adding this pilot aim to prepare for future studies.

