### **Participant Enrollment and Follow-Up**

We will enroll 620 subjects over the 2 seasons of recruitment and enrollment. To minimize withdrawal from the study, recruiters will aim to identify subjects who have a high likelihood of still being a LTC resident present in the same facility for the second blood draw. This will be an important criterion for inclusion into the study. This is generally the case with LTC residents because length of stay is on the time scale of months to years rather than days to weeks.

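### The plan promises 15% over-enrolment on 486 evaluable subjects (about 559) but states 500 randomised, which leaves room for only 2.8% without titers

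*Combined protocol and SAP*

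**What the plan says.** All references are to the combined protocol and SAP.

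- **Sample Size Considerations** fixes the number needed for the main strain: "To power the A/H3N2-specific analysis, we require 243 per vaccine group or 486 subjects total". It follows with "In order to achieve this sample size, we will overenroll by 15" per cent. It describes this allowance as based on earlier trial experience, and as adequate given the short gap between draws and the selection of subjects able to give all three samples.
- **Study design** sets the randomised cohort, allocated 1:1: "We propose a non-inferiority randomized clinical trial to enroll 500 Long Term Care residents age 65 and older". It then adds: "Up to an additional 120 subjects will be added to FLUBLOK substudy".
- **Participant Enrollment and Follow-Up** gives the overall total without a breakdown: "We will enroll 620 subjects over the 2 seasons of recruitment and enrollment".
- **Study procedures** says that FLUBLOK subjects "will not be part of the randomization process".
- **Recruitment for the FLUBLOK pilot arm for Year 2** sends further recruits to FLUBLOK once the recruitment goals for the primary comparison are met, but gives no number for those goals. Year 1 participants cannot re-enter the randomised comparison, but "these previously enrolled subjects would be eligible for recruitment on the FLUBLOK substudy".
- **Plan for obtaining informed consent** says: "Subjects who refuse the research blood draw will still remain in the study for data collection".

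**The concern.** The 15% is offered as the means of reaching 486, so 486 is the count wanted after losses and the randomised number should be about 15% larger. The only randomised number in the document is 500. The two statements cannot both describe the same trial.

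The reserve protects power for the strain and endpoint that set the sample size. A/H3N2 is the strain on which the plan chooses to power the trial, and the titer analysis needs more subjects than the seroconversion analysis (243 against 144 per group). If the reserve is not in the enrolment target, ordinary loss of samples takes that analysis below 80%. Subjects who refuse a draw stay in the study, so the enrolled count can reach its target while the count with titers falls short. A reader who relies on the 15% statement would believe the trial is protected against a loss that it is not sized for.

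**Working it through.** **Inputs.** 243 (titer) and 144 (seroconversion) per group for 80% power on A/H3N2, two-sided 95% CI, and 15% over-enrolment, all from Sample Size Considerations. 500 randomised 1:1 and up to 120 FLUBLOK, from Study design. 620 in total, from Participant Enrollment and Follow-Up.

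**1. The plan's own figure.** 2 × 243 = 486, as stated. The 243 itself cannot be rebuilt, because the plan gives neither the standard deviation of the log titer nor the assumed GMT ratio. It is taken as given here, and nothing below depends on those two values.

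**2. What 15% over-enrolment implies.**
- As an addition: 486 × 1.15 = 558.9, so 559. This covers a loss of 1 − 1/1.15 = 13.0%.
- As a loss rate: 486/0.85 = 571.8, so 572.

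**3. What 500 provides.**
- Margin over 486: 500/486 − 1 = 2.9%.
- Tolerable loss: (500 − 486)/500 = 14/500 = 2.8%, or 7 per arm if losses are even.
- Shortfall against step 2: 559 − 500 = 59, and 572 − 500 = 72.

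**4. Whether the 620 holds the reserve.** 500 + 120 = 620 exactly. The 120 are outside randomisation and cannot count toward 243 per randomised group.

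**5. Whether 500 could be the evaluable target.** 500 × 1.15 = 575, which appears nowhere either, and the plan states the requirement as 486.

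**6. Power when some of the 500 lack titers.** If n80 per group gives 80% power, then at n per group

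power = Φ[(z0.975 + z0.80) × √(n/n80) − z0.975] = Φ[2.8016 × √(n/n80) − 1.96].

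| Share without titers | Evaluable total | n per arm | Titer (n80 = 243) | Seroconversion (n80 = 144) |
|---|---|---|---|---|
| 0% | 500 | 250 | 81.1% | 95.8% |
| 2.8% | 486 | 243 | 80.0% | 95.3% |
| 5% | 475 | 237.5 | 79.1% | 94.9% |
| 10% | 450 | 225 | 76.9% | 93.8% |
| 13.0% | 435 | 217.4 | 75.5% | 93.1% |
| 15% | 425 | 212.5 | 74.5% | 92.6% |

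The table applies the same loss to both endpoints. The 5%, 10% and 15% rows are assumed loss rates. The 13.0% row is the loss that a 15% addition would cover.

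**The case against.** Three arguments can be made for the plan.

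First, 620 is a flat total and the FLUBLOK figure is only a ceiling. A randomised cohort of 559 to 572 with 61 to 48 FLUBLOK subjects would fit the 620, the ceiling and the 15%, and the goal that triggers diversion to FLUBLOK is not quantified. This reading is possible, but it contradicts the stated 500. It limits certainty about the sponsor's intention; it does not remove the inconsistency.

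Second, loss may be small. A refused draw is attempted again later. Recruiters look for residents likely to be in the same facility at the second draw, and subjects must be able to take part throughout. The GMT endpoint needs only the four-week sample, so missing the baseline or post-season draw does not by itself remove a subject from it. All of this stands, and actual loss could be below 15%. But the sponsor settled on 15% while citing the short interval and the subjects' ability to give the samples, so those conditions cannot also justify 2.9%.

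Third, the consequence is modest: about 5 points of power on one co-primary at the loss the plan allows for. That is correct, and it limits how serious the point is.

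**Conclusion.** The concern holds. The promised 15% margin is not in the stated randomised number: 500 is 2.9% above 486, and the shortfall is 59 to 72 subjects. Titer power for A/H3N2 is 81.1% with complete data, reaches 80% at 14 subjects lost, and is 75.5% to 74.5% at 13% to 15% loss. Seroconversion power is not threatened over this range. The effect is lower power only.

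This takes the plan's 243 and 144 per group as correct, assumes losses split evenly between arms, and reads the 620 as 500 plus 120. The true share without titers is unknown.

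Separately, the 80% is for the titer endpoint alone. If both A/H3N2 co-primaries must pass, power at 243 per group is 0.800 × 0.953 = 76.3% if the endpoints are independent, rising toward 80% as their positive correlation increases. That does not depend on the mismatch and adds no weight to it.

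**What to change.** Reconcile Study design, Sample Size Considerations, and Participant Enrollment and Follow-Up to one randomised target, and state how the 620 divides.

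**Option (a), sufficient by itself.** Keep 500 and delete the 15% statement. State that 500 tolerates 2.8% loss (14 subjects, evenly split) for 80% titer power and gives about 75% at 13% to 15% loss. This is a change of wording only; the cost is a less favourable stated power under attrition.

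**Option (b), if the reserve is wanted.** State a randomised target of 559 to 572, and use that number as the recruitment goal that must be met before further residents go to FLUBLOK. Holding the total at 620 leaves 620 − 559 = 61 to 620 − 572 = 48 FLUBLOK places. That fits a pilot with a ceiling of 120 and no power calculation. Keeping 120 FLUBLOK places instead raises the total to 679 to 692. In either case the extra 59 to 72 randomised subjects must be residents not enrolled in Year 1, since Year 1 participants can fill FLUBLOK places but cannot be randomised again. The cost is recruitment effort, and either a smaller pilot or a larger total.

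Whichever is chosen, say that the 80% refers to the A/H3N2 titer endpoint alone.

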### **Participant Enrollment and Follow-Up**

We will enroll 620 subjects over the 2 seasons of recruitment and enrollment. To minimize withdrawal from the study, recruiters will aim to identify subjects who have a high likelihood of still being a LTC resident present in the same facility for the second blood draw. This will be an important criterion for inclusion into the study. This is generally the case with LTC residents because length of stay is on the time scale of months to years rather than days to weeks.

### **Analysis Plan**

The FDA guidelines (listed above) for demonstrating non-inferiority for a seasonal flu vaccine dictate the analysis of the co-primary endpoints. The ratio of the geometric mean titers will be assessed using tests of means on the log-transformed titers. The upper limit of the 95% CI of the difference (HD – Fluad) in the mean log titer will be compared to  $\log(1.5)$ . The difference in the seroconversion rates will be assessed with a two-sample proportion test. The upper limit of the 95% CI of the difference (HD – Fluad) in the seroconversion rates will be compared to 0.1. These analyses will be performed on HAI titers of all three strains obtained from studies of pre- and post vaccination serum.

For practical recruitment purposes we have to run the study over 2 years to recruit sufficient numbers of the full cohort for A/H3N2 analysis based on the sample size calculation. At the conclusion of our study, we can summarize the A/H3N2 HAI titers and seroconversion for each year separately; but our non-inferiority hypothesis is powered based on combining the years to include the total enrolment for the A/H3N2 analysis. Since we will recruit enough subjects each year due to small number of subjects needed to power the A/H1N1 analysis, we will perform and report separate analysis for each year studied as well as combining the data. For the B strain we are underpowered and will combine the two years for this exploratory result.

We will perform analyses on the other assays (NAI and SVN) on samples obtained at pre- and post- vaccination from all 3 strains. We will run HAI on all 3 strains for the post-season blood draw for Aim 1 as a secondary analysis for differences in the ability of titers to hold in one vaccine vs. the other for the length of the season. We will also run the NAI on the A/H3N2 only (for feasibility to keep assay number reasonable) on the post-season sample to assess if there are differences in maintaining anti-NA titers between the two vaccines. Any statistical tests performed for these assays are not powered to detect superiority or non-inferiority while preserving our study-wise error rate and will be considered exploratory in nature.

Blood draws will be analyzed for humoral and cell mediated immune assays to determine flu-specific cells and antibody titers and immune status. Cells may be analyzed by RNAseq analysis to correlate aging immune responses and immune responses to the vaccines. We will not be making any DNA or doing any DNA gene analysis. No identifiable raw RNAseq files will be released that could be transcribed back to DNA for gene analysis purposes.

Analysis of FLUBLOK will be performed using the HAI and SVN assays as above and compared to the adjuvanted and high dose vaccines. NAI assays will not be used for this vaccine as it does not contain HA. If the pilot data are not powered by full non-inferiority studies we will also use Mann-U non-parametric tests to study differences in the mean responses between the vaccine groups.

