After a resident is consented and found still eligible, they will be randomized using the UH based study database, RedCap, to receive one of the two licensed study influenza vaccines. Subjects will be assigned a donor code at that time that does not indicate which vaccine they have received so the lab analysis can remain blinded. Study staff will bring enough supply of each vaccine for either type of randomization and maintain the cold chain according to pharmacy policy so unused vaccine can be returned to the UH monitored study refrigerator. Vaccine will be given by research nurse or physician study staff or the clinical nurse at the long term care facility, since it is a standard of care vaccine that would have been given by that nurse even if they are not in the study. The first blood draw will be up to 2 weeks prior to the vaccine, or right before the vaccine is given. All blood draws will be obtained by the study research nurse.

Then at 4 weeks +/- 3 days we will return and draw the second blood draw. The third blood draw will be obtained 2-4 weeks after the influenza season is over, based on the CDC

surveillance in our region for that season when rates are near the offseason baseline. Typically that means the final blood draw will be sometime in April or early May of each season.

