#### **Sample Size Considerations**

Due to the clinical importance of the A/H3N2 flu strain, we will focus this power analysis on the A/H3N2 strain. Between 1976 and 2007, the CDC estimates that on average three times more people died from influenza during A/H3N2-predominant seasons than in non-A/H3N2 predominant seasons (Centers for Disease and Prevention, 2010). Even the current A/H1N1 strain, which has circulated since 2009 as the pandemic 2009 A/H1N1 strain, is a less important

cause of morbidity and mortality in the elderly attributed to sustained pre-existing cross-reactive antibody titers to older strains that offer some protection (Hancock et al., 2009).

We used the criteria and comparisons proposed by FDA for a non-inferiority immunogenicity trial (FDA, 2007). They focus on changes in influenza antibody titers (our primary endpoint). The study should be adequately powered to assess the co-primary endpoints for HAI antibodies 1) post-vaccination geometric mean titer (GMT), and 2) seroconversion rates. Seroconversion is a 4-fold rise in GMT pre- to post-vaccination as long as pre-titer at least 1:10 and in pre-titer <1:10 for seroconversion the titers must achieve  $\geq 1:40$ .

To demonstrate non-inferiority in such a study:

- The upper bound of the two-sided 95% CI on the ratio of the GMTs (GMT HD vaccine/GMT Fluad) should not exceed 1.5.
- The upper bound of the two-sided 95% CI on the difference between the seroconversion rates (Seroconversion HD vaccine – Seroconversion Fluad) should not exceed 10%.

This power calculation will address both of those primary endpoints. No trials directly compare adjuvanted flu vaccine (Fluad) to HD flu vaccine or give sufficient detail in the same vaccination season to allow use of exactly the same flu strains. As a result, we must use the GMT and seroconversion data from two large trials each over 3500 subjects that compared Fluad or HD to the SD vaccine and that reported both GMT and seroconversion data (Falsey et al., 2009; Frey et al., 2014). Calculations were performed in R using the TrialSize package and power simulations were performed to confirm the results. The numbers below are the per-group sample sizes required for 80% power.

	Titer	Seroconversion
strain	analysis	analysis
H1N1	24	23
H3N2	243	144
B strain	571	168

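### The A/H3N2 GMT comparison, which sets the trial size, leaves out the pre-vaccination titer and season; an ANCOVA would gain precision at almost no cost

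*Combined protocol and SAP*

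**What the plan says.** Study Outcome Measures builds the GMT ratio from post-vaccination HAI titers. The Analysis Plan then says "The ratio of the geometric mean titers will be assessed using tests of means on the log-transformed titers" and compares the upper 95% limit of the HD minus Fluad difference with log(1.5). The criterion in Sample Size Considerations is "The upper bound of the two-sided 95% CI on the ratio of the GMTs (GMT HD vaccine/GMT Fluad) should not exceed 1.5".

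This endpoint fixes the trial size: "To power the A/H3N2-specific analysis, we require 243 per vaccine group or 486 subjects total". The A/H3N2 seroconversion analysis needs only 144 per group. The two seasons are pooled: "our non-inferiority hypothesis is powered based on combining the years to include the total enrolment for the A/H3N2 analysis". Summaries by year are also allowed for A/H3N2, but no section names a season term, a baseline covariate, a stratification factor or a regression model.

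The baseline is already measured. Study procedures says "We will obtain 20 ml of blood up to 2 weeks prior to the vaccine, or right before the vaccine is given", and the Analysis Plan says "These analyses will be performed on HAI titers of all three strains obtained from studies of pre- and post vaccination serum". The pre-titer also decides which seroconversion rule applies; for the low-titer branch the text is "and in pre-titer <1:10 for seroconversion the titers must achieve" at least 1:40.

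**The concern.** Two variables that may predict the post-vaccination titer, the pre-vaccination titer and the season, will be in the dataset but do not enter the GMT comparison. Variation in post-titer that they could explain stays in the error term and widens the confidence interval judged against 1.5.

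This is a loss of efficiency, not a bias. It matters because the endpoint is the one that sets the trial size, is planned at only 80% power, and has little slack. Sample Size Considerations promises 15% over-enrolment on 486, which is 486 × 1.15 = 559 or 486 / 0.85 = 572. The study design section randomises 500, which is 2.9% above 486.

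**Working it through.** **Inputs from the documents.** Two-sided 95% CI with only the upper limit used (one-sided 0.025), 80% power, margin 1.5, 1:1 allocation, 243 per arm.

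**Not in the documents, so assumed and varied.** The pre/post correlation r of log titers, the SD, the true ratio, the season shift and the share of missing pre-titers.

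**The plan's figure.** The 243 cannot be reproduced, because its SD and GMT inputs are not given. It can be back-solved. With z(0.975) + z(0.80) = 2.8016, the log10 SD is log10(1.5/R) / 2.8016 × √(243/2) for a true HD/Fluad ratio R. This gives 0.693 at R = 1.0, 0.530 at R = 1.1 and 0.381 at R = 1.2. The calculations below take 80% unadjusted power at 243 per arm as the starting point.

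**Adjusting for pre-titer.** The variance is multiplied by 1 − r². Power at 243 per arm is Φ(2.8016·√f − 1.96) with f = 1/(1 − r²), and the size needed for 80% is 243(1 − r²), rounded up.

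| r | 1 − r² | Power at 243 per arm | Per arm for 80% |
|---|---|---|---|
| 0.1 | 0.99 | 80.4% | 241 |
| 0.2 | 0.96 | 81.6% | 234 |
| 0.3 | 0.91 | 83.6% | 222 |
| 0.5 | 0.75 | 89.9% | 183 |
| 0.6 | 0.64 | 93.8% | 156 |

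**Coarse and floored titers.** A simulation used two-fold titers with 10–50% of pre-titers below 1:10 set to 5, scaled to about 80% unadjusted. The adjusted analysis gave 80.6–81.7%, 81.9–82.8%, 88.2–88.9% and 90.8–93.1% at underlying r = 0.2, 0.3, 0.5 and 0.6. Its false-positive rate at the margin was 2.3–2.7%. In a separate simulation with r = 0 and no season shift, adjusted and unadjusted power were both 80%.

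**Omitting season.** Suppose the SD behind 243 is a within-season SD and the seasons are equal in size. Pooling without a season term then gives f = 1/[1 + (log10 fold)²/(4·SD²)].

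| GMT shift between seasons | SD 0.70 | SD 0.53 | SD 0.38 |
|---|---|---|---|
| 1.5-fold | −0.6 points | −1.1 | −2.1 |
| 2-fold | −1.8 | −3.1 | −6.0 |

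If the SD behind 243 is instead a total SD that already includes the shift, the plan starts at 80% and a season term raises it. With f = 1/[1 − (log10 fold)²/(4·SD²)], power becomes 80.6% (1.5-fold, SD 0.70) to 86.2% (2-fold, SD 0.38).

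**Missing pre-titers.** With a share m missing, complete-case ANCOVA has f = (1 − m)/(1 − r²). Setting a missing covariate to its season mean has f = 1/(1 − (1 − m)r²). At m = 5% and r = 0.2 / 0.3 / 0.5, complete-case power is 79.6 / 81.7 / 88.4%, against 81.5 / 83.4 / 89.4% with the season-mean rule.

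**Combined simulation.** Within-season SD 0.53, 30% of pre-titers below 1:10, 5% missing and set to the season mean; the Monte Carlo error of the simulated powers is about 0.3–0.55 points.

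| Season shift | Analysis | r = 0.2 | r = 0.3 | r = 0.5 |
|---|---|---|---|---|
| 1.5-fold | Unadjusted | 78.4% | 78.4% | 77.9% |
| 1.5-fold | Adjusted | 80.4% | 82.1% | 87.5% |
| 2-fold | Unadjusted | 76.3% | 76.0% | 76.0% |
| 2-fold | Adjusted | 80.3% | 82.4% | 87.7% |

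False-positive rates at the margin were 2.5% adjusted and 2.5–2.6% unadjusted.

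**Thin slack.** If 15% of the 500 randomised were lost, about 212 per arm would remain. Unadjusted power is then about 74%, against 78% adjusted at r = 0.3 and 86% at r = 0.5.

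**The case against.** The strongest reply is that nothing here is wrong. A two-sample comparison of log titers is valid, its stated power is not refuted, and every figure for the gain rests on inputs the documents do not contain. At r = 0.1 to 0.2 the gain is only 0.4 to 1.6 points, and complete-case ANCOVA with 5% missing baselines at r = 0.2 falls just below 80%. The season loss assumes a within-season SD that the plan never states. The plan also says the FDA guidelines dictate the analysis. Finally, the current text already covers Year 2, so this would change a co-primary analysis mid-trial.

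Part of this stands. The gain is conditional and may be negligible, and the unadjusted figures below 80% in the combined simulation do not show a shortfall in the plan. The 5% missing share is purely illustrative: the consent section keeps subjects who refuse a draw, but does not say which draw.

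The rest does not change the conclusion. The season-mean rule removes the complete-case loss. Under either reading of the SD, a season term helps if the seasons differ. The criteria the plan lists fix the endpoints, the interval and the margins, and do not require an unadjusted estimate. The guidance itself was not available for this review, so that point needs confirming. The timing objection is real and calls for a lock point and a fallback.

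**Conclusion.** The point holds as one of efficiency. The endpoint that determines the sample size is analysed without two covariates that are already available. Starting from 80% at 243 per arm, adjustment for pre-titer alone gives between 80.4% (r = 0.1) and 93.8% (r = 0.6). Season contributes less, and only if GMTs differ between years. These figures assume a linear relation on the log scale and, for season, equal numbers per year.

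On the log scale under randomisation, the adjusted and unadjusted arm effects target the same GMT ratio, so the 1.5 margin carries over. The simulations showed no inflation of the false-positive rate and no loss of power when the baseline is uninformative. The seroconversion co-primary is unaffected.

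**What to change.** In the Analysis Plan:

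- Make the primary GMT analysis an ANCOVA of log post-titer on vaccine arm, log pre-titer and season. Exponentiate the arm coefficient as the adjusted HD/Fluad ratio and compare its upper 95% limit with the unchanged 1.5.
- Assign titers below 1:10 one fixed value, the same one used to compute the GMT.
- Keep a subject with a post-titer but no pre-titer by setting the covariate to the season mean over both arms. Never use that value to define seroconversion.
- Retain the unadjusted test as a sensitivity analysis.
- Confirm against the cited FDA guidance that an adjusted ratio is acceptable.

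Set this out in a dated amendment before any HAI results are linked to arm. The lock point must be written down because the only blinding described is for the laboratory: each subject gets "a donor code at that time that does not indicate which vaccine they have received so the lab analysis can remain blinded". If Year 1 results are already linked, keep the unadjusted test primary and report the ANCOVA as the sensitivity analysis.

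The cost is a little more analysis work and an amendment to a primary analysis after Year 1 enrolment. No subjects, visits or assays are added.
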